An initial appointment will then be arranged with each consenting adult. They will complete standardised health, OSA risk and activity questionnaires and have anthropometric measurements taken. The subset with RHT who also score ≥ 9 on the Epworth Sleepiness Scale (ESS) will be identified as 'at risk for OSA' and, will have, 24h ambulatory blood pressure monitoring (24hABPM) to confirm TRHT. For the subset with TRHT on the second appointment cardiorespiratory fitness will be measured using a six minute walk test (6MWT), and an echocardiogram will be completed. Sleep and physical activity monitoring for seven (24h) days/nights will then be undertaken using a wrist monitor to confirm sleep fragmentation. The outcome will be correlated with the ESS score to determine those at high risk of OSA.

As investigators will adhere to the new (2017) guideline for hypertension and include only those participants with TRHT, this will create a new knowledge dimension. The association between high risk of OSA and TRHT will be a key outcome measure. The outcomes from the echocardiogram, anthropometrics, activity parameters, and quality of life questionnaires will describe the population. The findings have potential to change the direction of research in the area, including opening the topic of TRHT to more debate and supporting modified guidelines for physicians and physiotherapists in managing the subpopulation with OSA and TRHT.

2. Background

Hypertension (HT) is a worldwide problem which affects at least one third of the adult population, numbering billions of people in the world.⁽¹⁾ Key determinants of the increasing prevalence of HT are increase in life expectancy, counterbalanced by factors such as an increase in both physical inactivity and obesity.⁽²⁾ Cardiovascular disease is the greatest cause of morbidity and mortality in New Zealand and the prevalence of HT in the adult population is over 30%, with ethnic disparities.^(3, 4) The Maori population is at a higher risk for HT compared to the other populations in New Zealand and has a higher use of antihypertensive medication - over 15% more than the New Zealand Europeans.⁽⁴⁾

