The population will comprise adults with resistant hypertension (RHT), based in the Dunedin region, aged 60 years and younger, who have been diagnosed with high blood pressure and are on three or more pharmacological agents of different classes including a diuretic. The population has been drawn from the Ministry of Health Pharmaceutical Collection Warehouse, via the Best Practice Advocacy Centre (bpac),⁽²³⁾ New Zealand.

The total number of adults with hypertension and being pharmacologically managed with three or more antihypertensive medications (estimated RHT) in New Zealand is 100,340; Southern District Health Board, 8425; and in the Dunedin region, 3184. The number of adults 60 years age or below in the Dunedin region with RHT is 559.⁽²⁴⁾

9. Eligibility Criteria

Inclusion criteria

- Age: 18-60 years inclusive
- Gender: all
- Able to communicate/follow instructions in English
- Based in Dunedin region
- Diagnosed with hypertension
- Prescribed three or more antihypertensive medications including a diuretic (RHT definition⁽⁹⁾).

Exclusion criteria

- Diagnosed with hypertension prescribed two or less antihypertensive medications
- Adults above the age of 60 years
- Diagnosed/known renal disease
- Females who are pregnant

10. Study Outcomes

Primary Outcome

The prevalence of TRHT in a population with RHT and the association of TRHT with high risk of OSA.

Secondary Outcome(s)

The correlation between increased Epworth Sleepiness Scale score and sleep fragmentation in the subset with true resistant hypertension.

11. Study Procedures

a. Recruitment of participants

Adults (18-60y) in the Dunedin region, [anonymized] on three or more pharmacological agents of different classes, and the general practices [anonymized] they are enrolled at, have been identified from the Ministry of Health Pharmaceutical Collection Warehouse, via the Best Practice Advocacy Centre (bpac),⁽²³⁾ New Zealand. The number of adults on the list is 559⁽²⁴⁾, [the list of names will remain de-identified to the research team as letters will be forwarded by General Practitioners].

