Following a briefing by researchers about the study at a scheduled meeting of the local General Practitioners Association, researchers will gain agreement from General Practitioners to distribute a letter to their patients identified from PWC database. The letter of invitation to participate in the study will be co-signed by [name] and Associate [name]. Inclusion criteria will be adults 18-60 years, who meet the definition for RHT⁽⁹⁾, have no known renal disease and are able to communicate in English. Based on the population with RHT in Dunedin region a sample size n=83, with 95% confidence interval and 10% margin of error, is required. The recruitment target is n=100 with the dropout rate of up to 20%.

A list of individuals who consent to participate in the study will be created and each will be matched with a random serial number generated by the computer (using MS Excel). NIH number/name and contact details will be included on the database but remain deidentified other than to the research group. The random ID number will be used in the study.

The proposed recruitment period is August 2018 to April 2019; 9 months

Step 1

For individuals identified with RHT.

August 2018 - invitation to participate in the study;

August 2018 – March 2019: initial recruitment, initial measurements, 24hABPM

Step 2

For the sub group identified with TRHT and high ESS score.

September 2018 – April 2019: Echo cardiogram, cardiorespiratory fitness test (6MWT) and 24h day/night activity monitoring for one week

October 2019 September 2020 – write up and publication

11b. Randomisation

The study is a descriptive observational trial.

11c. Study procedure

Step I – Initial recruitment

Potential participants will be invited to contact [name] with enquiries and to indicate their interest in participating in the study. The Principal investigator (PI), the PhD candidate, will provide each participant with an appointment time for the initial assessment where written informed consent will be obtained first. The session will be at the School of Physiotherapy. A summary of the stages of the study is outlined in Figure 1.

Step II – Assessment and measurements

Appointment 1:

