The PI will obtain the participant's demographic data (age; gender; ethnicity); general health and habits, physical activity level (initial assessment form – Appendix 1), quality of life (SF-36: Appendix 2) and OSA risk (ESS: Appendix 3), using self-administered questionnaires. Participants will use a tablet computer to complete this section which will take approximately 20 minutes. Data will then be downloaded onto the study data base (MS Excel).

The PI will then take the participant's resting blood pressure (office blood pressure – (BP)), heart rate, and peripheral saturation using standardised, calibrated equipment (NT1A Pulse oximeter, New Tech, Hamburg, Germany and Omron automatic digital blood pressure monitor, HEM 7322, Netherlands) and in accordance with the

ACC/AHA 2017 guidelines.⁽⁶⁾ Next, the PI will take the anthropometric (body weight, height and circumferences of neck, waist, hip,) measurements of the participant using standard guidelines⁽²⁵⁾ and equipment; electronic weighing scale (kg) and stadiometer (cm), measuring tape (scale in cm); with two decimal point accuracy. The equipment will be calibrated as required. This section of the procedure will take about 15 minutes. The variables, body mass index (BMI) and waist to hip ratio will be calculated using simple formulas on MS Excel.

The subset with RHT who also score ≥ 9 on the Epworth Sleepiness Scale (ESS) will be identified as 'at risk for OSA', and will be fitted with 24h ambulatory blood pressure monitor on the non-dominant upper arm, at the Cardiology Research Laboratory, on 9th floor in Dunedin Hospital. The participant will be advised to undertake daily activities/sleep as usual over the next 24 hours.

Appointment 2:

On the following day the device will be removed at the same setting, the Cardiology Research Laboratory, and data downloaded to confirm TRHT or not. Where TRHT is confirmed the participant will have an echo cardiogram to confirm baseline left ventricular function (results to be interpreted by co-investigator cardiologist).

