After the echocardiogram, the PI will conduct a Six Minute Walk Test (6MWT) following the standardised test and safety procedures. Then an activity monitor (ActiGraph GT3XPB, Pensacola, Florida⁽²⁶⁾) will be calibrated and placed on the non-dominant wrist to be worn for seven days/nights to determine the participant's true levels of functional activity during the day and during sleep. The participants will select the most convenient way to return the Activitrax monitor, either in person or by post. Data will be downloaded and analysed for activity levels, and sleep parameters, by the PI. Objective measurements of daytime activity (step count, time in low/moderate/vigorous physical activity, sedentary time and sleep, including total sleep time, awakenings, average awakenings, sleep efficiency, sleep onset, latency and wake after sleep onset) will be derived from the Actigraph calculator for the period.

The PI who will then determine the correlation between Epworth Sleepiness Scale score and sleep fragmentation and subsequently identify those with high risk of OSA in the subset with TRHT.

Note: Participants not found to have TRHT will meet with the co-investigator (Primary Supervisor) to discuss the outcomes and will be advised to visit their GP to discuss the report on findings for 24hABPM, risk of OSA (obtained from the questionnaire, ESS ≥ 9 ⁽²⁷⁾), and self-reported physical activity level). The participants with objective signs of OSA scored from the data downloaded from the activity monitor but not with TRHT

will be referred by the co-investigator cardiologist, to the physician at the Sleep Clinic for further sleep analysis.

Individuals who have TRHT and high risk of OSA will be invited to participate in a second study (Figure 1): a feasibility study to investigate the outcomes of a supervised physical activity programme on blood pressure levels.

[figure not shown]

Figure 1: Flow diagram Study 1 outlining measurements and data gathered at appointment 1 and appointment 2

11d. Measurement tools

The research nurse at the cardiology research laboratory will conduct the 24hABPM and echocardiography under supervision of the co-investigator/cardiologist in the project. Other measurements will be taken by the PI, who has experience in measuring anthropometry and cardiovascular parameters.

Table 1: Measurements, measuring equipment and tools

Measurements	Equipment/Tool

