Each participant will be allocated a random ID number generated using Microsoft Excel, by the PI, for use in the study.

Only the investigators (4 in number) will be able to access the data and the list of consenting participants. A research assistant may be involved in the study to assist the baseline collection of data and measurements. Hard copies will be stored securely in a locked filing cabinet, by the Primary Supervisor and the electronic data will be accessed under password protection for the period of 10 years.

No data will be individually represented and no individuals will be identifiable in the published data. Simple statistics will be used to publish the demographic data and no participant will be able to be identified by any other party or in any other publication.

14. Outcomes and Significance

Benefits for the participants

The participants will be able to receive a report (Ambulatory blood pressure, echocardiogram, risk of obstructive sleep apnoea (ESS score), physical activity level, anthropometry such as BMI, Hip to waist ratio) on their cardiovascular health. If they indicate 'yes' on the consent form, a copy will also be forwarded to their GP.

Participants not found to have TRHT will meet with the co investigators (Primary supervisor) to discuss the outcomes and will be advised to visit their GP to discuss the report on the findings for 24hABPM, risk of OSA (obtained from the questionnaire, ESS ≥ 9), and self-reported physical activity level. The participants with a high risk of OSA will be referred by the co-investigator cardiologist, to the physician at the Sleep Clinic for further sleep analysis.

Participants who are identified with both TRHT and high risk of OSA, in the study, will be invited to participate in a second study, a single group non randomised intervention

study to determine the effects of a 12 week physical exercise program on 24h ABPM. The exercise as part of lifestyle modification is recommended to manage TRHT.⁽⁷⁾

Significance

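### Individual high risk of OSA is derived from a group correlation, which classifies nobody, and the ESS ≥ 9 gate cannot supply the missing label

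*Protocol*

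**What the plan says.** Three parts of the protocol bear on this point.

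- **How high risk is assigned.** Section 11c, Appointment 2, says the investigator will "determine the correlation between Epworth Sleepiness Scale score and sleep fragmentation and subsequently identify those with high risk of OSA"; this applies to participants with TRHT. The Introduction is more direct: "The outcome will be correlated with the ESS score to determine those at high risk of OSA".
- **Who reaches that step.** Section 11c, Appointment 1, restricts the 24h monitor by ESS score: "The subset with RHT who also score ≥ 9 on the Epworth Sleepiness Scale (ESS) will be identified as 'at risk for OSA', and will" (the sentence ends with the fitting of that monitor). Step 2 in section 11a, which includes the week of activity monitoring, is headed "For the sub group identified with TRHT and high ESS score".
- **Where the label is used.** The primary outcome in section 10 is "The prevalence of TRHT in a population with RHT and the association of TRHT with high risk of OSA". Sections 11c and 14 also use high risk to decide who is invited to the second study, and section 14 uses it for referral.

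The secondary outcome in section 10 is "The correlation between increased Epworth Sleepiness Scale score and sleep fragmentation in the subset with true resistant hypertension". Sections 11c and 11d list several actigraphy sleep measures. None is named as the fragmentation measure and none has a cut-off. The only numeric OSA criterion is ESS ≥ 9; the feedback text in 11c and 14 repeats it as "risk of OSA (obtained from the questionnaire".

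**The concern.** The protocol does not merely leave high risk of OSA for later definition. It states a method, and the method gives no result for any individual. A coefficient of 0.1 or 0.8 describes the group and leaves each participant unlabelled. It would also tie a primary-outcome variable to the result of a secondary hypothesis.

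Someone would have to supply a working definition once the ESS and sleep data were in hand, and that choice would shape the reported association and the membership of the second study.

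A lesser issue is that the ESS ≥ 9 gate cuts off the lower part of the ESS scale before the correlation is computed. A small r in that group could be misread as no relation between sleepiness and fragmentation in TRHT generally.

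**Working it through.** **1. The plan's own figure.** The protocol gives no sample size for the correlation. Its n = 83 reproduces as a prevalence calculation with p = 0.5 (assumed), a 10% margin and a population of 559:

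- n0 = 1.96² × 0.25 / 0.10² = 96.04
- n = 96.04 / (1 + 95.04/559) = 82.08, rounded up to 83

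This covers precision of a proportion in all RHT participants, not the correlation in a subset.

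**2. Can the stated rule label a person?** Its inputs are pairs of ESS and fragmentation values, and its output is a single r. Nothing in the Introduction, 11c, 11d or 12b turns r, or a person's own fragmentation value, into a yes/no status.

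**3. Can ESS ≥ 9 fill the gap?** Under 11c, 24hABPM is given only when ESS ≥ 9, so everyone with known TRHT status has the indicator equal to 1. Its variance is zero, and no association between TRHT and that indicator can be estimated. Equating high risk with ESS ≥ 9 would also leave the Appointment 2 step with nothing to do.

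**4. Effect of the gate on r (illustration).** The ESS distribution is not in the documents. Assume it is roughly normal over the full range with mean μ = 6-12 and SD σ = 4-5, cut at 8.5 because scores are whole numbers, and linearly related to fragmentation with equal residual variance.

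- a = (8.5 − μ)/σ; λ = φ(a)/(1 − Φ(a)); u² = 1 + aλ − λ², where u is the ratio of restricted to full ESS SD
- r′ = r·u / √(1 − r² + r²u²)

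For r = 0.4:

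| μ, σ | a | λ | u | r′ |
|---|---|---|---|---|
| 6, 4 | 0.625 | 1.234 | 0.499 | 0.213 |
| 8, 5 | 0.100 | 0.863 | 0.585 | 0.247 |
| 12, 4 | −0.875 | 0.336 | 0.770 | 0.319 |

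The range is about 0.21-0.32. If r = 0, then r′ = 0. Under the same linear model, the slope of fragmentation on ESS is unchanged by selecting on ESS.

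**5. Consequence for power.** For 80% power at two-sided 5%, N = ((1.96 + 0.84)/atanh r)² + 3. This gives 47 for r = 0.40, 75 for r = 0.32 and 176 for r = 0.21. The assumed distributions put about 27-81% of people at ESS ≥ 9. If 30-70% of those have TRHT (also assumed), 83 participants leave between 83 × 0.27 × 0.30 ≈ 7 and 83 × 0.81 × 0.70 ≈ 47 people for the correlation.

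**The case against.** The best defence is that the word *subsequently* in 11c describes a separate, later step, and that 11c mentions OSA signs scored from each monitor, which suggests an individual assessment was intended. Figure 1 and the appendices are not visible. This softens 11c but does not rescue the rule: the Introduction makes the correlation the means of deciding, and no individual criterion appears in the visible text.

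A reader might infer that the protocol holds two conflicting definitions of OSA risk. It does not quite. ESS ≥ 9 is called *at risk*, high risk is a later tier after actigraphy, and the feedback text carrying ESS ≥ 9 concerns participants without TRHT. The fault is that the second tier is undefined.

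A reader might also infer that the secondary correlation is biased toward zero. That presumes a target over the full ESS range. Section 10 speaks of an increased ESS score and Step 2 of a high one, so r within ESS ≥ 9 may be the intended quantity, although the objectives and hypotheses do not carry that restriction. If the true correlation is zero, truncation creates no bias. What stands is that the estimate is conditional and the target ambiguous.

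Section 12b plans regression with ESS score, and ESS still varies above 9. That analysis remains possible in the gated sample, but it does not define high risk.

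**Conclusion.** The point holds for the classification rule. The Introduction and 11c assign an individual status from a group statistic that cannot provide it, and the one existing threshold cannot stand in because it is constant among those with known TRHT status. This rests on the protocol text alone and needs no numerical assumption. It matters because the label enters the primary outcome and decides who is invited to the second study.

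The range restriction is a caveat on interpretation, not a demonstrated bias. Its direction for a non-zero linear relation follows from selecting on ESS. Its size (r = 0.4 falling to about 0.21-0.32) depends wholly on the assumed ESS distribution, linearity and equal residual variance.

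The text on who is measured is also inconsistent. Step 1 in 11a lists 24hABPM for RHT participants generally, while 11c restricts it to ESS ≥ 9. Section 11c also refers to monitor findings in people without TRHT, although it gives the activity monitor only after TRHT is confirmed. Neither passage provides a clear route for ESS below 9 into the correlation.

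**What to change.** Separate the two tasks.

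1. **Classification.** In the Introduction and 11c, replace the correlation rule with one per-person definition of high risk of OSA, fixed before data are seen. Base it on one named actigraphy parameter already collected, with a cut-off chosen by the investigators, and keep it distinct from *at risk* (ESS ≥ 9).
2. **Correlation.** In 12b, report the ESS-fragmentation correlation separately with a 95% CI and state that it is conditional on ESS ≥ 9. Give the regression slope beside it. Do not read a small r as evidence of no correlation over the full ESS range. A range-restriction correction should be at most a sensitivity analysis: it assumes linearity, equal residual variance and the same ESS spread in TRHT as in all enrolled participants.
3. **Consistency.** Reconcile 11a and 11c on who receives 24hABPM and activity monitoring.

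Items 1 and 2 change wording only and need no new measurements. The cost is a narrower conclusion about the correlation.

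They do not solve everything. A correlation over the full ESS range would need 24hABPM, and actigraphy in those with TRHT, among people with ESS below 9, which is a change of procedure. An association of TRHT with ESS-defined risk cannot be estimated within the gated sample. If activity monitoring is confined to TRHT, the new label will be known only there and will have no comparison group, so item 3 also decides whether the association in the primary outcome can be estimated.

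### The Sleep Clinic referral in 11c reaches nobody as written: it needs activity-monitor findings without TRHT, but the monitor is fitted only after TRHT is confirmed; Section 14 states a different rule

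*Protocol*

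**What the plan says.** The Protocol describes the use of the wrist monitor in three places.

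- **Introduction.** "For the subset with TRHT on the second appointment cardiorespiratory fitness will be measured using a six minute walk test (6MWT"; the next step but one reads "Sleep and physical activity monitoring for seven (24h) days/nights will then be undertaken using a wrist monitor to confirm sleep fragmentation".
- **11a, timetable.** Step 2, which contains the echocardiogram, the walk test and one week of activity monitoring, is headed "For the sub group identified with TRHT and high ESS score".
- **11c, Appointments 1 and 2.** 24-hour ambulatory monitoring (ABPM) is fitted to "The subset with RHT who also score ≥ 9 on the Epworth Sleepiness Scale (ESS". After the download, "Where TRHT is confirmed the participant will have an echo cardiogram to confirm baseline left ventricular function". Then "After the echocardiogram, the PI will conduct a Six Minute Walk Test (6MWT", and last comes the monitor, "placed on the non-dominant wrist to be worn for seven days/nights".

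Referral is described in two places.

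- **11c, Note after Appointment 2.** The cardiologist refers to the Sleep Clinic "The participants with objective signs of OSA scored from the data downloaded from the activity monitor but not with TRHT". The same Note gives participants without TRHT a results meeting and advice to see their GP. It offers those with TRHT and high risk of OSA a place in a second study.
- **Section 14, benefits for the participants.** The cardiologist refers participants at high risk of OSA to the Sleep Clinic. Neither TRHT status nor the monitor is mentioned. The sentence comes directly after one about participants without TRHT.

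**The concern.** The 11c referral combines two conditions that the study's own order of procedures keeps apart: having monitor data, and not having TRHT. Staff who follow 11c alone would refer nobody on objective sleep findings. The people left out are those whose sleep was actually recorded. That sits badly with the Background, which describes OSA as closely tied to resistant hypertension and as its most commonly cited secondary cause.

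Section 14 does not settle the matter, because it states another criterion and does not make clear whom it covers. One promised piece of clinical follow-up is thus governed by two rules, and what a participant receives depends on which section is followed.

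**Working it through.** The Protocol gives no figure for this referral, so there is none to reproduce. The check is one of logic and rests on no assumed rate.

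**Inputs**, all from the Protocol:
1. ABPM is given only if ESS ≥ 9 (11c, Appointment 1).
2. Echocardiogram, walk test and monitor follow only if ABPM confirms TRHT (11c, Appointment 2; 11a, Step 2; Introduction).
3. 11c referral = monitor signs of OSA AND not TRHT (11c, Note).

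**Enumeration**

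| ESS ≥ 9 | TRHT | ABPM | Monitor | Can meet the 11c referral |
|---|---|---|---|---|
| no | no | no | no | no: no monitor data |
| no | yes (not tested) | no | no | no: no monitor data |
| yes | no | yes | no | no: no monitor data |
| yes | yes | yes | yes | no: excluded by TRHT |

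Monitor data exist in 1 of 4 combinations. The referral condition is met in 0 of 4.

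**Does the result depend on who has ABPM?** Step 1 of the 11a timetable could be read as ABPM for everyone with resistant hypertension. That would change the ABPM column only. The monitor would still follow confirmed TRHT, so the count stays at 0.

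**Does other text support monitoring in TRHT only?** Yes. The sleep-fragmentation objective (Section 4), hypothesis (5b) and secondary outcome (Section 10) are all set within the TRHT subset. The 11c Note lists what participants without TRHT take to their GP: the ABPM finding, the ESS-based risk and self-reported activity. It lists no monitor result.

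**Does other text point the other way?** Yes, in one place. Section 12b plans to describe sleep and activity in the population with resistant hypertension, and to relate activity and sleep to TRHT by regression. That regression needs monitor data from people without TRHT, and no procedure in the Protocol collects them.

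**11c against Section 14.** The Protocol uses two terms. ESS ≥ 9 makes a participant at risk. High risk is determined later, from ESS together with sleep fragmentation, within the TRHT subset (11c, sentence before the Note). Taken literally with that meaning, Section 14 refers participants with TRHT at high risk, exactly the people whom 11c excludes. A reader who carries the limit to non-TRHT over from the preceding sentence would instead arrive at the same empty group as 11c.

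**The case against.** The best defence is that the two outcomes were meant as a division: participants with TRHT and high risk go on to the second study, and those without TRHT but with signs of OSA go to the Sleep Clinic. This would explain the exclusion, and 12b suggests that wider monitoring may have been in mind. Figure 1 is not shown and could depict it. What stands is that the error may lie in the monitoring sequence and not in the referral sentence. It does not rescue the text: three places give the monitor only after TRHT, and a figure showing otherwise would contradict them. An invitation to an exercise study is not further sleep analysis, and Section 14 contains no such exclusion.

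Stronger claims are tempting, but the documents do not support them.

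- A reader might infer that participants with TRHT and fragmented sleep have no route to the Sleep Clinic at all. Section 14, read literally, already covers them. The empty group belongs to 11c.
- A reader might list many possible Section 14 referral groups by counting ESS ≥ 9 as high risk. The Protocol keeps the two terms apart, so only the ambiguity of scope remains.
- A reader might conclude that participants with TRHT receive no feedback. Section 14 offers participants a report that includes ABPM, echocardiogram and OSA risk, with a copy to the GP if they agree. Figure 1, the consent form and the information sheet are not available, so silence elsewhere proves nothing.

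**Conclusion.** The point holds in this form: the 11c referral is met in 0 of 4 combinations of ESS and TRHT, and it excludes the one combination with objective sleep data. Section 14 states a different rule of unclear scope. The zero follows from the Protocol's visible text and its order of procedures. It rests on no assumption about how many participants score ≥ 9 or have TRHT. The Protocol gives neither rate, so the number of people affected cannot be stated.

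This is a contradiction in wording with consequences for participant care and uniform conduct. As the plan stands, it affects no estimate and no sample size. Participants without TRHT who score ≥ 9 are not left without provision, since they have the results meeting and GP advice.

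**What to change.** 1. In the 11c Note, delete the last four words of "The participants with objective signs of OSA scored from the data downloaded from the activity monitor but not with TRHT", so that any participant with monitor signs of OSA is referred whatever their TRHT status.
2. In Section 14, state the same rule, with high risk of OSA meaning ESS plus sleep fragmentation as in 11c, and say that it applies to all participants with monitor data.
3. Leave the GP advice for participants without TRHT and with ESS ≥ 9 as it is. No new ESS cut-off is needed.
4. If the sponsor meant participants without TRHT to wear the monitor too, as 12b suggests, correct the sequence in the Introduction, the 11a timetable and 11c Appointments 1 and 2, and still make the deletion in item 1.
5. Check Figure 1 and the participant documents for agreement.

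Items 1 to 3 cost a wording change in two sections and possibly a few more Sleep Clinic referrals. Item 4 would add seven days of monitor wear for each participant without TRHT. It would supply data for the 12b regression, so estimates could change under that option alone. The sample size does not change under either.
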